8.3. Concomitant and Other Medications

8.3.1.1. Tabulation of time on PrEP and ART

Tabulations of PrEP and ART will use the following assessments:

- Adherence to HIV medications as reflected in viral suppression among participants living with HIV, assessed by chart review of HIV RNA levels conducted as standard clinical care and reported on CRFs.

8.4. Tolerability

Tolerability is assessed through:

- Self-reported response to whether a participant did not take doxycycline because of side effects.
- Report of early termination due to side effects of study drug.

Descriptive: The Likert scale responses will be tabulated for each study visit for each cohort.

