1.2.1 Doxycycline Safety

Several features of doxycycline make it an optimal choice for STI PEP. Doxycycline has been used safely and for extended durations as prophylaxis against infections such as malaria²³ and for non-infectious conditions including rosacea²⁴ and acne vulgaris.²⁵ Doxycycline is generally safe and well-tolerated when used chronically. Side effects include mild gastrointestinal symptoms, photosensitivity, and rarely pill esophagitis and pseudotumor cerebri.²⁶ Reassuringly, doxycycline has a much lower risk than other antibiotics for the antibiotic-associated diarrhea caused by C. difficile infection,^{27, 28} and may even exert a protective effect against C. difficile.^{29, 30} Doxycycline is a scalable PEP intervention, as it is generic, inexpensive, and widely available. Doxycycline does not require dose adjustment in hepatic or renal failure, including dialysis. In the IPERGAY doxycycline PEP study, there was no difference in grade 3 or 4 adverse events between the study arms. As anticipated, there were more gastrointestinal side effects in those on PEP (25%) vs. the non-PEP control arm (14%). Discontinuation of doxycycline was uncommon with 8 study participants (7%) stopping doxycycyline due to side effects attributed to doxycycline, the majority of which were gastrointestinal.¹ Given the safety profile of doxycycline and the enrollment of participants receiving ongoing clinical care for HIV or HIV PrEP, study-specific monitoring will be limited to complete blood count and liver function tests at months 3 and 9 to assess for hematologic and hepatic toxicity, which occur rarely with chronic doxycycline use (<1%). Assessment for side effects (eq., pill esophagitis. photosensitivity, new onset headaches), with clinical and laboratory testing if indicated if potential serious adverse events are suspected. Participants will receive standard of care monitoring through their HIV or PrEP. Typical standard of care monitoring for PLHIV includes semi-annual viral load monitoring, renal and liver function tests, and annual CBC. Typical standard of care monitoring for PrEP patients includes guarterly HIV tests and semi-annual or annual renal monitoring.

1.2.2 Rationale for single dose doxycycline as STI PEP.

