6 CLINICAL AND LABORATORY MONITORING

6.1 Schedule of Events

Month (+2/-10 week window)	0	3	6	9	12 or Termination visit	Doxycycline initiation visit for those in control arm
Informed consent	\checkmark					\checkmark
Smartphone app instructions	\checkmark					
Review of current medications		$\sqrt{*}$	$\sqrt{*}$	$\sqrt{*}$	$\sqrt{*}$	\checkmark
Antibiotic & STI history	\checkmark	\checkmark	\checkmark	\checkmark		
Meningococcal vaccination history						
Sexual behavior questionnaire	\checkmark	\checkmark	\checkmark	\checkmark	\checkmark	
Dispense pills/adherence counseling*	$\sqrt{*}$	$\sqrt{*}$	$\sqrt{*}$	$\sqrt{*}$		\checkmark
Doxycycline pill count and adherence recall*		$\sqrt{*}$	$\sqrt{*}$	$\sqrt{*}$	√*	
Doxycycline PEP acceptability survey*			$\sqrt{*}$		$\sqrt{*}$	
General symptom assessment	\checkmark	\checkmark	\checkmark	\checkmark		
Costing questionnaire		\checkmark	\checkmark	\checkmark		
Condoms/lubricant	\checkmark	\checkmark	\checkmark	\checkmark		
Risk reduction counseling	\checkmark	\checkmark	\checkmark	\checkmark		
GC/CT testing (throat & rectal swab, urine collection)	\checkmark	\checkmark		\checkmark	\checkmark	
Syphilis testing	\checkmark	\checkmark	\checkmark	\checkmark	\checkmark	
Rectal swabs stored for future microbiome testing, all participants	\checkmark		\checkmark		\checkmark	\checkmark
Rectal swab stored for future MG testing	\checkmark	\checkmark	\checkmark	\checkmark	\checkmark	
Urine stored for future MG testing (also at time of symptomatic urethritis)	\checkmark	\checkmark	\checkmark	\checkmark	\checkmark	
Swabs/urine at time of evaluation for STI symptoms or confirmed STIs for resistance testing		at time	e of evalua	ation for S	STI symptoms or	r confirmed STI
Anterior nares and oropharyngeal swabs for Staphylococcus aureus culture	\checkmark		\checkmark		\checkmark	
Oropharyngeal swabs for cultures of Neisseria species	\checkmark				\checkmark	
Stool sample from first 50 PLWH & first 50 HIV- on PrEP*	$\sqrt{*}$		$\sqrt{*}$		√*	
Collection of hair for doxycycline testing			\checkmark		\checkmark	

DoxyPEP protocol Ver 9.0 5/27/2022

(subset of participants, optional) *Inter	*Intervention arm only **Standard of care arm only						
Qualitative interviews*				3-12	2 months	• •	
Weight	\checkmark	\checkmark	\checkmark	\checkmark			
Reimbursement	\checkmark	\checkmark	\checkmark	\checkmark			
Stored serum for future testing (Optional)	\checkmark				\checkmark		

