6.3 Instructions for evaluations

6.3.1 **Smart phone application**: A smartphone application (app), Blackbook, (developed in conjunction with UCSF researchers) currently in use to track sexual behavior and PrEP use in young MSM has been adapted for use in this study to measure daily sexual risk practices (both study arms) and doxycycline PEP administration (intervention arm only). Study staff will assist with obtaining smartphones through local available resources such as Lifeline Assist, which make cell phones available to qualifying lower income individuals, when needed and feasible (https://www.truconnect.com/lifeline/freephone/signup). Participants will be given unique codes to permit download of the app from an online resource and guidance on how to use the application.

- 6.3.2 **Review of current medications**: All participants will have current medications reviewed at screening for possible drug interaction with doxycycline. At subsequent quarterly visits, participants randomized to doxycycline PEP will have current medications be reviewed and any new medications will be assessed for possible drug interactions.
- 6.3.3 **STI symptom screen**. Participants will be asked about current STI symptoms including dysuria, rash, throat pain, rectal pain/discharge, and genital lesions
- 6.3.4 **Symptom assessment**. At each visit, participants in both study arms will be asked about possible doxycycline side effects, including esophagitis, rash, gastrointestinal symptoms, photosensitivity, headache, and changes in vision (including blurred, double vision, vision loss). Control arm participants will be asked about these symptoms to establish a comparator for non-specific symptoms which can occur in the absence of doxycycline.
- 6.3.5 **Antibiotic and STI history**: History will be recorded of any non-study provided antibiotics taken in the last 3 months and any STI diagnosis in preceding 3 months, including the diagnosis of urethritis requiring treatment but without detection of gonorrhea or chlamydia. At study entry, STI history for preceding 12 months will be recorded as well as obtained through chart review when possible.
- 6.3.6 **Meningococcal vaccination history**: At study entry and at month 12, receipt of any prior meningococcal vaccination and the type (if known) will be recorded, using a checklist that will include
 - Serogroup A only (includes MenAfriVa, PsA-TT)
 - Serogroup B only (includes Trumenba, Bexsero)

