10 STATISTICAL CONSIDERATIONS

10.1 Outcome measures

10.1.1 Primary outcome:

Combined incidence of GC, CT, or early syphilis infection by laboratory- based diagnosis (e.g., positive GC or CT based on NAAT, syphilis based on four-fold increase in non- treponemal titers or positive darkfield on exudate from a lesion). Incident STI diagnoses will be ascertained through the study through periodic testing, interim visits for STI symptoms, as well as STI surveillance from the San Francisco and King County Departments of Health and by medical records provided for participants who receive their care from other clinical sites.

10.1.2 Secondary outcomes:

- Safety of doxycycline PEP, measured by evaluation of all Grade 3 and 4 AEs attributed to study medication.
- Tolerability, measured using a brief quarterly questionnaire administered to both intervention and control groups evaluating side effects commonly associated with doxycycline as well as recording any discontinuations of doxycycline by participants and their reasons.
- Acceptability, assessed through a brief questionnaire for all PEP recipients administered at month 6 and 12 and in-depth structured qualitative interviews for a subset, conducted within 6 months of month 12 visit. A separate consent will be provided for the in-depth qualitative interview at the time of this interview.
- Doxycycline coverage of sexual contacts in the prior 3 months, ascertained by sexual behavior and doxycycline

use from the web-based app, augmented by quarterly adherence questionnaires and pill counts.

- Longitudinal exposure to doxcycyline will be assessed using hair collection, with a semiquantitive evaluation in the control arm (doxycycline present vs. absent) and in the PEP arm (doxycycline concentration high vs. low).
- Adherence to HIV medications as reflected in viral suppression among participants living with HIV, assessed by chart review of HIV RNA levels conducted as standard clinical care.
- Discontinuation of PrEP, based on self-report
- Residual hair samples of participants without HIV infection on PrEP will be archived for future tenofovir testing to measure adherence to Truvada PrEP.

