2.2.2.2. Safety, tolerability and acceptability of doxycycline PEP

- Safety: All grade 2 and higher hematologic and hepatic laboratory abnormalities, all grade 3 and 4 adverse events judged to be associated with doxycycline (possibly, probably, or definitely related), and all SAEs.
- Tolerability: in person quarterly assessments of discontinuations of doxycycline, discontinuation of PEP, symptom assessment, and self-reported side effects questionnaire at 6 and 12 months by CASI (computer assisted self-interview),

In person assessment by research staff at scheduled visits to include:

- All permanent doxycycline discontinuation and reasons for discontinuation;
- For all temporary doxycycline interruptions ≥ 7 days, reason for interruption; and
- Side effects:
 - o presence/absence of the following symptoms and if present, whether attributed to doxycycline (if taking) by a) participant and b) investigator: rash, sunburn, headache, change in vision, pain with swallowing, diarrhea, nausea, vomiting, abdominal pain, or other.

CASI questions related to tolerability

- At least once in the past 3 months, I did not take doxycycline within 3 days after sex because I wanted to avoid side effects. (Reported using 5-point Likert scale)
- Were there any other reasons that you did not take doxycycline within 3 days after sex? Yes/No (Y/N) and open-ended response if yes is selected.
- In the past 3 months, do you feel that taking doxycycline affected your sexual experience? (Reported using 3-point scale: negative, neutral, positive effect).

• Acceptability: self-reported acceptability questionnaire by CASI for all doxycycline PEP recipients administered at month 6 and 12.

Answer to the following questions, reported using a 5-point Likert scale, unless otherwise indicated

- Doxycycline is easy to take.
- I'm worried that taking doxycycline will cause antibiotic drug resistance. (reverse coded)
- I'm worried that doxycycline will hurt my body. (reverse coded)
- Taking doxycycline PEP will reduce my condom use. (reverse coded)
- Doxycycline has other good effects for me.
- Taking doxycycline PEP has helped me take my PrEP or ART more regularly.
- A sexual partner has expressed negative feelings about me taking doxycycline. (reverse coded)
- A sexual partner has expressed positive feelings about me taking doxycycline
- Taking doxycycline only when needed after sex and not every day is... (5-point scale from very unacceptable to very acceptable)

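### SAP 8.4 gives no analysis of the symptom checklist collected in both arms as a tolerability endpoint; it analyses only two items that exist in people given doxycycline

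*SAP*

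**What the plan says.** **Protocol.** Section 10.1.2 defines the outcome as "Tolerability, measured using a brief quarterly questionnaire administered to both intervention and control groups evaluating side effects commonly associated with doxycycline", together with discontinuations of doxycycline and their reasons. Section 6.3.4 has both arms asked about possible side effects at each visit and gives the reason: "Control arm participants will be asked about these symptoms to establish a comparator for non-specific symptoms which can occur in the absence of doxycycline". In the schedule of events (6.1), the row "General symptom assessment" carries no intervention-arm-only asterisk.

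**SAP, endpoint.** Section 2.2.2.2 lists the in-person symptom record among the tolerability measures: "presence/absence of the following symptoms and if present, whether attributed to doxycycline (if taking) by a) participant and b) investigator". The qualifier about taking the drug makes sense only if people not on doxycycline are asked too. The symptoms named are rash, sunburn, headache, change in vision, pain on swallowing, diarrhea, nausea, vomiting, abdominal pain and other.

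**SAP, analysis.** Section 8.4 says tolerability is assessed through two items: "Self-reported response to whether a participant did not take doxycycline because of side effects" and "Report of early termination due to side effects of study drug". The only output it describes is a tabulation of the Likert responses by visit and cohort. Arm is not mentioned, and neither is the checklist.

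**The concern.** The endpoint section and the analysis section of the SAP do not match. A checklist named as a tolerability endpoint, with a control group questioned expressly to give a background rate, has no planned summary. The two items that are analysed ask a participant who knows they are on doxycycline whether a skipped dose or a stop was due to side effects. An untreated control cannot answer either.

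Tolerability is part of the first secondary objective in both documents. Protocol 1.2.8 also gives tolerability data as a goal of follow-up after early closure and calls the resulting information critical to judging risk and benefit. Headache, diarrhea and rash also occur without doxycycline. Without the control rate, a reader cannot tell how much of what is reported on drug is excess.

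**Working it through.** The point rests on setting the texts side by side. The documents state no figure that needs reproducing, and the arithmetic below is illustration only.

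**1. Does any other text supply the missing analysis?**

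- SAP 8, opening: safety and tolerability are assessed in the ITT cohort or in the doxycycline arm alone. This permits a by-arm display but does not say which item uses which population, and it specifies no symptom table.
- SAP 8.1.2 and 8.1.3: grade 2 and higher hematologic and hepatic AEs are tabulated by grade and arm, and SAEs are listed by cohort and arm. These are randomised safety data, but not the checklist.
- SAP 7.1: tabulation by arm within cohort, but under Efficacy.
- SAP 11.1: the table list is marked as unfinished. Its one safety-section row uses the Safety population, which SAP 5.2.2 expects to coincide with the doxycycline arm.
- Protocol 10.5 (analyses after closure to enrollment): STI incidence, resistance, adherence and acceptability, with no symptom comparison.

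None of them closes the gap.

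**2. How large could the background share be?** Inputs are gastrointestinal side effects of 25% on PEP and 14% in controls in the earlier trial (protocol 1.2.1).

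Background share = control rate / on-drug rate = 14/25 = 56%. Holding the on-drug rate at 25%, control rates of 5%, 10%, 14% and 20% give shares of 20%, 40%, 56% and 80%.

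**3. How precise would a by-arm difference be?** Difference = 0.25 − 0.14 = 0.11, and SE = √[p₁(1−p₁)/n₁ + p₀(1−p₀)/n₀].

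- The 554 enrolled at interim review (protocol 1.2.8), assumed split 2:1 as 369 and 185: SE = √(0.1875/369 + 0.1204/185) = 0.0340; 0.11 ± 1.96 × 0.0340 gives 4.3 to 17.7 points.
- Planned totals of 520 and 260 (twice the 260 and 130 per cohort in SAP 3.3.1): SE = √(0.1875/520 + 0.1204/260) = 0.0287; 5.4 to 16.6 points.
- Planned, one cohort (260 and 130): 3.0 to 19.0 points.

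The first line is the relevant one, because enrollment stopped early. It covers both cohorts together and allows nothing for control time lost to rollover. The protocol does not say over what period the 25% and 14% were counted, so they do not forecast any single visit.

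**4. Why not an ever-reported proportion?** Control follow-up without doxycycline ends at rollover (protocol 1.2.8 and 6.3.24), while doxycycline participants continue to month 12. Suppose, purely to show the direction, that doxycycline had no effect, every visit carried a 14% symptom risk independently, and controls contributed two visits against four. The ever-reported proportions would be 1 − 0.86² = 26.0% and 1 − 0.86⁴ = 45.3%, an apparent excess of 19.3 points produced by unequal follow-up alone. Per-visit proportions do not have this fault.

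**The case against.** The strongest reply is that nothing has been removed. The checklist is still collected and is still an endpoint in SAP 2.2.2.2. SAP 8 allows ITT tabulation, SAP 1 says the document may evolve before database lock, and the table list is unfinished. The early-termination item reflects the discontinuation half of the protocol's own definition. The SAP was written against protocol 5.0, so the comparator sentence, read here in version 9.0, cannot be confirmed for the version the SAP followed. All of this is fair. It limits the point to an omission in the analysis section, but 8.4 as written still departs from the endpoint list in the same SAP, whichever protocol version applies. The rollover came after the SAP, so its absence there is a matter for updating.

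Three stronger readings are tempting, and the documents do not support them:

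- A reader might infer that background symptoms will be reported as drug effects. That would need a symptom table for the doxycycline arm alone, and none is planned: 8.4 tabulates symptoms for neither arm.
- A reader might infer that the plan uses no randomised evidence on harms. SAP 8.1.2 and 8.1.3 already present selected laboratory AEs and SAEs by arm.
- A reader might infer that a control column would settle attribution. Both arms know their assignment, so a difference in reports mixes drug effect with expectation.

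SAP 8 also plans no statistical tests for adverse event comparisons. That is no obstacle to a descriptive table.

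**Conclusion.** The concern holds as a gap between a listed secondary endpoint and its analysis. The symptom checklist has no planned summary in either arm, and the two items in 8.4 have no control counterpart. Followed as written, the tolerability conclusion would rest on open-label attribution without the randomised comparison that the protocol set up.

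The size in this trial cannot be derived from the documents. The 56% background share and the interval of about 4 to 18 points assume that the earlier trial's gastrointestinal rates apply, that the 554 split 2:1, and that no control time is lost. They show that the comparison would be informative, not what it would find. The change should be made, but the primary efficacy analysis is unaffected.

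**What to change.** In SAP 8.4, add a descriptive table of each symptom listed in 2.2.2.2, in the ITT population, by randomised arm, scheduled visit and cohort. Give per-visit proportions and unadjusted risk differences with 95% CIs, without hypothesis tests, in keeping with SAP 8.

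- Show control visits after rollover to doxycycline separately. Protocol 6.3.24 already records the start date on a CRF.
- Do not use a proportion reporting a symptom at any post-baseline visit unless follow-up is equal between arms.
- Keep the two existing items as doxycycline-arm descriptives.
- State beside the table that it supplies a background rate and does not remove open-label reporting bias.

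The cost is one table and a short SAP revision. No new data, visits or participants are needed.

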8.5. Acceptability

Acceptability is assessed in the doxycycline PEP arm only via a seven-question acceptability questionnaire using a 5-point Likert scale.

Descriptive: The scales will be converted to an acceptability score—using reverse coding where appropriate—and summarized by cohort, site, and visit. Individual questions will also be reported in detail.

9. ADDITIONAL SECONDARY ENDPOINT ANALYSIS

9.1. Coverage of sex acts

Coverage of sexual contacts and accompanying doxycycline use is assessed by CASI at 6 and 12 months, and also assessed in the mobile app.

These self-report endpoints reflect coverage:

- 1) In the past 3 months, I missed taking doxycycline within 3 days after sex at least once. Y/N
- 2) In the past 3 months, when you have had anal or vaginal/frontal without using a condom the whole time, how often did you take doxycycline PEP within 72 hours after sex? 5-point scale
- 3) In the past 3 months, when you have given or received oral sex, how often did you take doxycycline PEP within 72 hours after oral sex? 5-point scale
- 4) The last time you had anal or vaginal/frontal sex without using a condom the entire time, did you take doxycycline? Y/N
- 5) The last time you had oral sex did you take doxycycline. Y/N

Descriptive: Each endpoint will be tabulated by visit for the doxycycline PEP arm. Five-point scales will be dichotomized by combining “always/most of the time” vs. categories that are less often.

Blackbook: App-acquired data will be used to compute the proportion of sex acts covered by doxycycline PEP for each participant for all periods when the app was used, and the participant remained on study drug.

Descriptive:

- 1) Participant use of the app will be summarized: number/proportion using the app, number of weeks in use, compared to number of weeks of doxycycline PEP, proportion of time described by App use; also summarized by study quarter.
- 2) Proportion of sex acts covered by doxycycline PEP for all person-time collected in each quarter will be summarized.

9.2. Gut resistome sub-study

Analysis of the gut resistome will be described in a separate statistical analysis plan.

10. REVISIONS TO THE SAP

Not Applicable

11. APPENDIX

11.1. Table of Contents for Data Reports

Appendix to be completed

Title	Population	Comments
Study Population Section		
	ITT	Unique
	ITT	Unique
	ITT	Unique
	ITT	Repeat 9.3.1
Efficacy Section		
Figures		
	ITT	Unique
	ITT	Unique
Tables		
	ITT	Unique
	ITT	Unique
	ITT	Repeat 12.1.2.1
	ITT	Unique
	ITT	Unique
	ITT	Unique
Safety Section		
	Safety	Unique

Listings

	Title	Population	Comment
	Subject Enrollment Information	Enrolled	Unique
	Subject Disposition	Safety	Unique
	Subjects who did not Satisfy Inclusion/Exclusion Criteria (if applicable)	Screening Failure	Unique
	Protocol Deviations	Safety	Unique
	Listing of Relationship of Serious Adverse Event Body Systems, Group Terms, and Verbatim Text	Safety	Unique

